14.1.1 Assessment of the Impact of COVID-19 on Adverse Events

The relationship of selected AEs to COVID-19 will be assessed by investigator as detailed in the DMP Appendix B. Each of the primary safety analyses described in [Section 14.1](#) will be additionally summarized by relationship to COVID-19 (Not related to COVID-19 vs. Related to COVID-19).

14.2 Clinical Laboratory Variables

Clinical laboratory tests are performed at Baseline, Week 12, and Week 52/ET visits. In general, laboratory test results are from a central laboratory. Due to COVID-19 disruptions it is possible that some test results may be collected from a local laboratory. A separate eCRF will capture local laboratory results in order to facilitate medical monitoring of subject safety. Local laboratory results will not be included in any summary data analysis; they will, however, be included in data listings, as well as a separate local laboratory PCI listing. All results (central and local) will be displayed in Système International [SI] units. It is encouraged, but not required, that clinical labs be completed under fasting conditions.

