14.2.5.3 Potentially Clinically Important Laboratory Values

The number and percentage of subjects with potentially clinically important (PCI) laboratory values at scheduled post-Baseline visits and overall post-Baseline will be summarized by Baseline status (all or within normal range) for selected parameters. PCI criteria are listed in [Table 5](#) and [Table 6](#). Subjects with multiple PCI values for a given parameter will be counted only once for that parameter. All post-Baseline values will be considered, including unscheduled and out of window values. PCI tables will be presented for OL timepoints only using OL Baseline, and DB+OL timepoints using the DB Baseline from the antecedent study (see [Section 5.2](#) and [Table 4](#)).

For the by-visit summary, the numerator for the percentage is the number of subjects with a post-Baseline PCI value for the given parameter, visit, and cohort, and the denominator is the number of subjects with non-missing values for the given parameter, visit, and cohort. For the overall post-Baseline summary, the numerator for the percentage is the number of subjects with at least 1 post-Baseline PCI value for the given parameter and cohort, and the denominator is the number of subjects with at least 1 post-Baseline value for the given parameter and cohort. For hemoglobin, hematocrit and uric acid, the count and percentage of subjects with PCI values will be presented for each gender as well as for both genders combined. A listing of all PCI values in study ACP-103-047 will be provided. This listing will include all observations from study ACP-103-047 for those subjects and parameters for which at least one PCI value (including OL Baseline) was observed.

Table 5 Criteria for Potentially Clinically Important Laboratory Values – Hematology and Chemistry

Analyte	Conventional Unit	Low PCI Criteria	High PCI Criteria	SI Unit	Low PCI Criteria	High PCI Criteria
Hematology (whole blood)						
Hemoglobin (male)	g/dL	<11	>18	g/L	<110	>180
Hemoglobin (female)	g/dL	<10	>17	g/L	<100	>170
Hematocrit (male)	%	<30	>55	L/L	<0.3	>0.55
Hematocrit (female)	%	<30	>50	L/L	<0.3	>0.5
Leukocyte (White Blood Cell Count)	x 10 ³ /uL	≤2.8	≥15	x 10 ⁹ /L	≤2.8	≥15
Neutrophils	x 10 ³ /uL	≤1.5	No upper limit	x 10 ⁹ /L	≤1.5	No upper limit
Platelet Count	x 10 ³ /uL	≤75	≥700	10 ⁹ /L	≤75	≥700
Chemistry (serum or plasma)						
ALT (SGPT)	U/L	No lower limit	≥3 X ULN	U/L	No lower limit	≥3 X ULN

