14.3 Vital Signs

Vital signs are assessed at Baseline and Weeks 2, 4, 8, 12, 16, 28, 40 and Week 52/ET visits.

Due to COVID-19 disruptions it may be necessary for vital signs to be collected outside of the clinic by persons other than study site staff. These results will not be included in any summary data analysis; they will, however, be presented in data listings, and in a separate PCI listing of vitals measured by persons other than study site staff.

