14.3.2 Vital Signs Methods of Analysis

Vital signs will be summarized using descriptive statistics at Baseline and all scheduled post-Baseline visits. The change from Baseline values will also be summarized at the scheduled post-Baseline visits.

Vital sign values will be considered PCI if they meet the criteria listed in [Table 7](#). The number and percentage of subjects with post-Baseline vital signs that are PCI will be

summarized at scheduled post-Baseline visits and for overall post-Baseline. For the overall post-Baseline summaries, all post-Baseline values will be considered, including unscheduled and out of window values. Subjects with multiple PCI values for a given parameter will be counted only once for that parameter. For the by-visit summary, the numerator for the percentage is the number of subjects with a post-Baseline PCI value for the given parameter, visit and cohort, and the denominator is the number of subjects with non-missing values for the given parameter, visit and cohort. For the overall post-Baseline summary, the numerator for the percentage is the number of subjects with at least 1 post-Baseline PCI value for the given parameter and cohort, and the denominator is the number of subjects with at least 1 post-Baseline value for the given parameter and cohort.

Vitals change from Baseline and PCI tables will be presented for OL timepoints only using OL Baseline, and DB+OL timepoints using the DB Baseline from the antecedent study (see [Section 5.2](#) and [Table 4](#)).

A listing of all PCI values will be provided (excluding those vitals collected by persons other than study site staff). There will be a separate PCI listing for vitals collected by persons other than study site staff. These listings will include all observations for those subjects and parameters for which at least one PCI value (including Baseline) was observed

Table 7 Criteria for Potentially Clinically Important Vital Signs

Vital Sign Parameter	Unit	Criteria ^a		
		Observed Value	And/Or	Change Relative to Baseline
Systolic blood pressure (supine or sitting)	mmHg	≥180	And	Increase of ≥20
		≤90	And	Decrease of ≥20
Diastolic blood pressure (supine or sitting)	mmHg	≥105	And	Increase of ≥15
		≤50	And	Decrease of ≥15
Pulse (supine or sitting)	bpm	≥120	And	Increase of ≥15
		≤50	And	Decrease of ≥15
Weight	kg	Not Applicable		Increase of ≥7%
				Decrease of ≥7%

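### Potentially clinically important (PCI) values from local laboratories, or from vital signs taken by non-site staff, are listed but not counted, so some subjects with a known PCI value are tabulated as having none

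*SAP*

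**What the plan says.** **Laboratory tests (SAP 14.2).** Results normally come from a central laboratory. The SAP allows that COVID-19 disruption may send some tests to a local one. For those, "Local laboratory results will not be included in any summary data analysis". They go into data listings, "as well as a separate local laboratory PCI listing". Central and local results are both to be shown in SI units.

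**Vital signs (SAP 14.3 and 14.3.2).** The SAP foresees that disruption may require "vital signs to be collected outside of the clinic by persons other than study site staff". The rule is again "These results will not be included in any summary data analysis", and "There will be a separate PCI listing for vitals collected by persons other than study site staff".

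**Overall laboratory PCI percentage (SAP 14.2.5.3).** The numerator counts each subject who has one or more PCI results after Baseline on that test, within cohort. As for what it is divided by, "the denominator is the number of subjects with at least 1 post-Baseline value for the given parameter and cohort". SAP 14.3.2 builds the vital-sign percentage in the same way.

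**Number of chances to be counted.** Laboratory tests have two scheduled post-Baseline visits (Week 12 and Week 52/ET). Vital signs have eight.

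No supplementary table or footnote brings the barred PCI values back into a count.

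**The concern.** In a by-visit table a barred value leaves numerator and denominator together. The overall table works differently, because one eligible value at any post-Baseline visit keeps the subject in the denominator. Take a subject with a central non-PCI result at Week 12 and a local PCI result at Week 52. The table shows that subject as free of PCI, while the sponsor's own listing flags the value.

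Long-term safety is the primary objective, and the overall PCI percentage is the figure a reader will take away for laboratory tests and vital signs. For subjects of this kind the error can only lower the count. Laboratory tests are the more exposed, because losing one of two draws matters more than losing one of eight visits.

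**Working it through.** The plan has no figure to reproduce. The study is descriptive, its sample size is not power-based, and neither document gives a PCI rate or a share of barred results. The check has two parts: applying the counting rule to examples, and sizing the effect under stated assumptions.

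**1. The counting rule applied to four constructed subjects (laboratory)**

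| Subject | Post-Baseline values | Central-only table | All sources |
|---|---|---|---|
| A | central non-PCI, local PCI | counted, no PCI | PCI |
| B | local PCI only | omitted | PCI |
| C | central PCI, local non-PCI | PCI | PCI |
| D | two central non-PCI | counted, no PCI | no PCI |

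The SAP rule gives 1/3 and all sources give 3/4. The subjects were chosen to show the two routes, not to represent a rate. Subject A is misclassified. Subject B leaves the table. Omissions can move the percentage either way, because dropping a subject whose only values are local and non-PCI raises it.

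**2. Size for laboratory tests**

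Assumptions: every subject has both draws, Week 12 is central, a share q of Week 52 draws is local, and each draw is PCI with probability p.

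*Independent draws:*
- All sources: 1 − (1 − p)²
- As tabulated: p + (1 − p)·p·(1 − q)
- Relative understatement: q(1 − p)/(2 − p), which is close to q/2 for small p

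| p | q | All sources | As tabulated | Relative understatement |
|---|---|---|---|---|
| 3% | 10% | 5.91% | 5.62% | 4.9% |
| 3% | 30% | 5.91% | 5.04% | 14.8% |
| 5% | 10% | 9.75% | 9.28% | 4.9% |
| 5% | 30% | 9.75% | 8.33% | 14.6% |

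*Fully persistent status:* a subject who is PCI at Week 52 was already PCI at the central Week 12 draw. Both percentages equal p and the understatement is 0.

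**3. Expected number of misclassified subjects per laboratory parameter**

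With independent draws this is N·q·p·(1 − p). N is 353 (rollovers at the second interim analysis, SAP 16.1) or 750 (planned enrolment, SAP 3.5).

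| p | q | N = 353 | N = 750 |
|---|---|---|---|
| 1% | 5% | 0.17 | 0.37 |
| 3% | 10% | 1.03 | 2.18 |
| 5% | 25% | 4.19 | 8.91 |

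**4. Size for vital signs**

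Assumptions: eight independent visits, p = 3% per visit, and exactly one visit barred in 10% of subjects.
- All sources: 1 − 0.97⁸ = 21.63%
- Lost: 0.10 × 0.03 × 0.97⁷ = 0.24 percentage points
- As tabulated: 21.38%
- Relative understatement: 0.24/21.63, about 1%

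**The case against.** The exclusion is prespecified, disclosed and defensible as a main analysis. A weight or blood pressure taken by someone other than site staff and compared with a clinic Baseline could meet the change criteria in SAP Table 7 spuriously. The barred values stay visible: the PCI listings show every observation for an affected subject and parameter. An abnormal laboratory finding may also be reported as an adverse event (Protocol 7.2.1), and treatment-emergent adverse events are the primary measure. The stated reason for local testing is pandemic disruption, not the subject's result, so a barred draw behaves much like a missed one, and the overall denominator already tolerates missed draws.

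Most of this stands, and it is why the single-source tables should remain. It does not settle the point. With a missed draw the value is unknown; here it is known and flagged. Adverse-event reporting depends on the investigator and does not correct the PCI count.

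A reader might also infer that the SAP contradicts itself, because 14.2.5.3 says "All post-Baseline values will be considered, including unscheduled and out of window values". The text does not support that reading: the sentence concerns the timing of values, and the explicit source rule in 14.2 governs.

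**Conclusion.** The point holds as a limited one. A subject with at least one eligible non-PCI value and a PCI value from a barred source is tabulated as having no PCI, and nothing else in the SAP corrects this. The effect on the overall percentage cannot be determined from the documents. For laboratory tests it lies between 0 and about 5–15% in relative terms if 10–30% of Week 52 draws were local. The upper figures are essentially half the assumed local share, and they need independent draws with both present in every subject. For vital signs the illustration gives about 1%, so the laboratory range must not be carried over.

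Three stronger inferences are not supported:

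- **That PCI incidence is known to be biased low.** The SAP says only that local testing is possible and gives no share. Subjects with barred values only are omitted, not counted as free of PCI.
- **That all out-of-clinic vital signs are barred.** The bar covers only those taken by persons other than site staff. Out-of-clinic ECGs are not barred; SAP 14.4 has them centrally read when possible.
- **That the PCI values are concealed.** They are listed.

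This is an inexpensive improvement to reporting, not a flaw in the main analysis.

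**What to change.** Keep the central-only laboratory tables and the site-staff-only vital-sign tables as the main analysis. For the open-label period, add to the overall post-Baseline PCI summaries one supplementary count per parameter, labelled *any PCI value including local-laboratory results / vital signs taken by non-site staff*. Its denominator should be the subjects with at least one post-Baseline value from any of those sources, so that subjects with barred values only are included.

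The by-visit tables can stay as they are. Restricting the addition to the open-label period avoids needing local data from the antecedent study, which these documents do not describe.

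The cost is modest extra programming across parameters and cohorts. The values are already captured, and their PCI listings are already planned. Table 5 uses multiples of the upper limit of normal or fixed limits, so its criteria can be applied to local results. The downside is mixed measurement sources in the supplementary count, which the label discloses.

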14.2.1 Chemistry

Clinical chemistry serum tests include the following:

- Sodium (Na), potassium (K), chloride (Cl), phosphorus (P), calcium (Ca),, blood urea nitrogen (BUN), creatinine (CR), uric acid, , bicarbonate
- Alanine aminotransferase (ALT), aspartate aminotransferase (AST), gamma-glutamyl transpeptidase (GGT), alkaline phosphatase (ALP), total bilirubin (TBIL), lactate dehydrogenase (LDH)
- Glucose
- Albumin (ALB), total protein
- Creatine kinase (CK)/creatinine phosphokinase (CPK)

14.2.2 Miscellaneous

- Prolactin
- Lipid panel
 - total cholesterol, HDL-cholesterol, LDL-cholesterol, triglycerides, very low density lipoprotein cholesterol

14.2.3 Hematology

Hematology tests include the following:

- Complete blood count (CBC) including:
 - White blood cell (WBC) count, absolute neutrophil count, complete differential (relative and absolute), hematocrit (Hct), hemoglobin (Hgb), red blood cells (RBC), platelets, reticulocyte count

14.2.4 Urinalysis

Urinalysis tests include the following:

- Blood, RBCs, WBCs, protein, glucose, ketones, specific gravity, pH, leukocyte esterase
- A urine pregnancy test should be performed at all designated visits for women of childbearing potential
 - If urine cannot be obtained in women of childbearing potential, a serum pregnancy test should be done in its place
- Urine drug screen will be performed at Baseline, Week 12, and Week 52

14.2.5 Methods of Analysis for Clinical Laboratory Variables

14.2.5.1 Observed Values and Change from Baseline

Clinical laboratory values reported as continuous values for hematology, chemistry and urinalysis will be summarized using descriptive statistics at Baseline and scheduled post-Baseline visits. The change from Baseline values will also be summarized at scheduled post-Baseline visits. The overall minimum and maximum post-Baseline observed and change from Baseline values will also be summarized (for OL study period only).

For hemoglobin, hematocrit and uric acid, by-visit as well as post-OL Baseline minimum and maximum will be presented for each gender as well as for both genders combined.

For urinalysis with categorical results, the number and percentage of subjects will be tabulated by category at Baseline and each scheduled post-Baseline visit. For the categorical urinalysis by-visit summary, the denominator is the number of subjects with non-missing values for the given parameter, visit, and cohort.

Summaries of the above will also be presented for OL timepoints only using OL Baseline, and DB+OL timepoints using the DB Baseline from the antecedent study (see [Section 5.2](#) and [Table 4](#)).

14.2.5.2 Shift Tables

Laboratory values will be summarized in shift tables to determine the number and percentage of subjects with values classified as below (low), within (normal), or above (high) normal ranges at each scheduled post-Baseline visit relative to the same classification at the Baseline visit. Shift tables will be presented for shift from OL Baseline as well as shift from DB Baseline. For the by-visit shift summary, the denominator is the number of subjects with non-missing values at Baseline and the given visit for the given parameter and cohort.

The shifts from Baseline to overall post-Baseline minimum and overall post-Baseline maximum will also be presented. The denominator is the number of subjects with non-missing Baseline and at least 1 post-Baseline value for the given parameter and cohort.

For hemoglobin, hematocrit and uric acid, by-visit as well as post-Baseline minimum and maximum will be presented for each gender as well as for both genders combined.

Shift tables will be presented for OL timepoints only using OL Baseline, and DB+OL timepoints using the DB Baseline from the antecedent study (see [Table 4](#)).

14.2.5.3 Potentially Clinically Important Laboratory Values

The number and percentage of subjects with potentially clinically important (PCI) laboratory values at scheduled post-Baseline visits and overall post-Baseline will be summarized by Baseline status (all or within normal range) for selected parameters. PCI criteria are listed in [Table 5](#) and [Table 6](#). Subjects with multiple PCI values for a given parameter will be counted only once for that parameter. All post-Baseline values will be considered, including unscheduled and out of window values. PCI tables will be presented for OL timepoints only using OL Baseline, and DB+OL timepoints using the DB Baseline from the antecedent study (see [Section 5.2](#) and [Table 4](#)).

For the by-visit summary, the numerator for the percentage is the number of subjects with a post-Baseline PCI value for the given parameter, visit, and cohort, and the denominator is the number of subjects with non-missing values for the given parameter, visit, and cohort. For the overall post-Baseline summary, the numerator for the percentage is the number of subjects with at least 1 post-Baseline PCI value for the given parameter and cohort, and the denominator is the number of subjects with at least 1 post-Baseline value for the given parameter and cohort. For hemoglobin, hematocrit and uric acid, the count and percentage of subjects with PCI values will be presented for each gender as well as for both genders combined. A listing of all PCI values in study ACP-103-047 will be provided. This listing will include all observations from study ACP-103-047 for those subjects and parameters for which at least one PCI value (including OL Baseline) was observed.

Table 5 Criteria for Potentially Clinically Important Laboratory Values – Hematology and Chemistry

Analyte	Conventional Unit	Low PCI Criteria	High PCI Criteria	SI Unit	Low PCI Criteria	High PCI Criteria
Hematology (whole blood)						
Hemoglobin (male)	g/dL	<11	>18	g/L	<110	>180
Hemoglobin (female)	g/dL	<10	>17	g/L	<100	>170
Hematocrit (male)	%	<30	>55	L/L	<0.3	>0.55
Hematocrit (female)	%	<30	>50	L/L	<0.3	>0.5
Leukocyte (White Blood Cell Count)	x 10 ³ /uL	≤2.8	≥15	x 10 ⁹ /L	≤2.8	≥15
Neutrophils	x 10 ³ /uL	≤1.5	No upper limit	x 10 ⁹ /L	≤1.5	No upper limit
Platelet Count	x 10 ³ /uL	≤75	≥700	10 ⁹ /L	≤75	≥700
Chemistry (serum or plasma)						
ALT (SGPT)	U/L	No lower limit	≥3 X ULN	U/L	No lower limit	≥3 X ULN
AST (SGOT)	U/L	No lower limit	≥3 X ULN	U/L	No lower limit	≥3 X ULN
Total Bilirubin	mg/dL	No lower limit	≥1.5 ULN	umol/L	No lower limit	≥1.5 ULN
BUN	mg/dL	No lower limit	≥30.0	mmol/L	No lower limit	≥10.71
Creatine Kinase (CK)	U/L	No lower limit	≥3 ULN	U/L	No lower limit	≥3 ULN
Sodium	mEq/L	≤125	≥155	mmol/L	≤125	≥155
Potassium	mEq/L	≤3.0	≥5.5	mmol/L	≤3.0	≥5.5
Calcium, total	mg/dL	<8.0	>11.0	mmol/L	<2.0	>2.75
Lactate Dehydrogenase (LDH)	U/L	No lower limit	≥3 X ULN	U/L	No lower limit	≥3 X ULN
Alkaline Phosphatase	U/L	No lower limit	≥3 X ULN	U/L	No lower limit	≥3 X ULN
Uric acid (male)	mg/dL	No lower limit	≥10.5	umol/L	No lower limit	≥624.75
Uric acid (female)	mg/dL	No lower limit	≥8.5	umol/L	No lower limit	≥505.75
Albumin	g/dL	≤2.6	≥6.0	g/L	≤26	≥60
Total Protein	g/dL	≤5.0	≥10.0	g/L	≤50	≥100
Chloride	mEq/L	≤85	≥120	mmol/L	≤85	≥120
Glucose (random)	mg/dL	≤45.1	≥200.0	mmol/L	≤2.48	≥11
Serum Creatinine	mg/dL	Not Applicable	>1.5 ULN	umol/L	Not Applicable	>1.5 ULN
Triglycerides	mg/dL	Not Applicable	>300	mmol/L	Not Applicable	>3.39
Gamma-Glutamyl Transferase (GGT)	U/L	Not Applicable	≥3 ULN	U/L	Not Applicable	≥3 ULN

Table 6 Criteria for Potentially Clinically Important Laboratory Values - Urinalysis

Urinalysis	Low PCI Criteria	High PCI Criteria
Blood (occult blood)	Not Applicable	≥Moderate
Protein	Not Applicable	≥100 mg/dL
Glucose	Not Applicable	≥500 mg/dL

14.2.5.4 Data Listings

All laboratory test results will be listed. The listings will include date and study day of collection. Out of range values will be flagged in the data listings (e.g., as ‘L’ or ‘H’). Central and local laboratory values will be presented separately.

A listing of all PCI values will be provided. This listing will include all observations for those subjects and parameters for which at least one PCI value (including Baseline) was observed. Central and local laboratory PCI listings will be presented separately.

The pregnancy results (positive or negative) for female subjects of childbearing potential will be presented in a listing.

14.3 Vital Signs

Vital signs are assessed at Baseline and Weeks 2, 4, 8, 12, 16, 28, 40 and Week 52/ET visits.

Due to COVID-19 disruptions it may be necessary for vital signs to be collected outside of the clinic by persons other than study site staff. These results will not be included in any summary data analysis; they will, however, be presented in data listings, and in a separate PCI listing of vitals measured by persons other than study site staff.

14.3.1 Vital Signs Variables

Vital signs include weight, height (measured at Screening of antecedent study), derived BMI, sitting systolic blood pressure (SBP), sitting diastolic blood pressure (DBP), pulse rate, temperature, and respiratory rate. The sitting blood pressure should be measured after the subject has been sitting for ≥3 minutes.

14.3.2 Vital Signs Methods of Analysis

Vital signs will be summarized using descriptive statistics at Baseline and all scheduled post-Baseline visits. The change from Baseline values will also be summarized at the scheduled post-Baseline visits.

Vital sign values will be considered PCI if they meet the criteria listed in [Table 7](#). The number and percentage of subjects with post-Baseline vital signs that are PCI will be

summarized at scheduled post-Baseline visits and for overall post-Baseline. For the overall post-Baseline summaries, all post-Baseline values will be considered, including unscheduled and out of window values. Subjects with multiple PCI values for a given parameter will be counted only once for that parameter. For the by-visit summary, the numerator for the percentage is the number of subjects with a post-Baseline PCI value for the given parameter, visit and cohort, and the denominator is the number of subjects with non-missing values for the given parameter, visit and cohort. For the overall post-Baseline summary, the numerator for the percentage is the number of subjects with at least 1 post-Baseline PCI value for the given parameter and cohort, and the denominator is the number of subjects with at least 1 post-Baseline value for the given parameter and cohort.

Vitals change from Baseline and PCI tables will be presented for OL timepoints only using OL Baseline, and DB+OL timepoints using the DB Baseline from the antecedent study (see [Section 5.2](#) and [Table 4](#)).

A listing of all PCI values will be provided (excluding those vitals collected by persons other than study site staff). There will be a separate PCI listing for vitals collected by persons other than study site staff. These listings will include all observations for those subjects and parameters for which at least one PCI value (including Baseline) was observed

Table 7 Criteria for Potentially Clinically Important Vital Signs

Vital Sign Parameter	Unit	Criteria ^a		
		Observed Value	And/Or	Change Relative to Baseline
Systolic blood pressure (supine or sitting)	mmHg	≥180	And	Increase of ≥20
		≤90	And	Decrease of ≥20
Diastolic blood pressure (supine or sitting)	mmHg	≥105	And	Increase of ≥15
		≤50	And	Decrease of ≥15
Pulse (supine or sitting)	bpm	≥120	And	Increase of ≥15
		≤50	And	Decrease of ≥15
Weight	kg	Not Applicable		Increase of ≥7%
				Decrease of ≥7%

^a A post-baseline value is considered as a PCI value if it meets both criteria for observed value and change from baseline.

